Procedural steps	
Procedural steps for the Corrie Digital Health group:
 
 a. Patients presenting with acute myocardial infarction as the primary diagnosis for admission to a participating site, and meeting other eligibility criteria, will be recruited b. Participants must be approved to participate in this research study by his/her primary care team 
 - As resources allow, to make participation possible for participants who are not iPhone owners, we will offer an "iShare" device share program wherein we loan an iPhone along with the Apple Watch during the study period - We will also introduce a family and friends program wherein we offer the app (but not Apple Watch) to family and friends who have an iPhone and would like to use the app for the purpose of supporting the participant (participant must agree and designate the family/friend, including email and phone number, in the app) c. If the participant passes screening questions for study inclusion (i.e., owns a

smartphone and not limited from normal smartphone usage due to conditions such as visual, motor, auditory impairment), the participant will proceed to e-Consent

d. e-Consent will be done through ResearchKit on a study iPad

e. The study team member will be present to guide the participant and give the participant an opportunity to ask questions before having the participant sign the consent form. If consent is provided, a Corrie sign will be placed on the door or in the room to indicate study participation to clinical staff or an Epic research flag will be placed.

f. Next, the study team member will guide the participant through download of the app, and setup of the app including inputting medications and profile information. Participants will also be given a StartKit (See Supplemental Study Documents) which will include information on how to use the app to reference following discharge.

g. Consenting participants will be given an Apple Watch, Silicone Healthband, and iHealth blood pressure monitor (FDA approved), and will be instructed to wear the Apple Watch/Silicone Healthband on their non-dominant wrist. The Apple Watch and iHealth blood pressure monitor will be paired with the iPhone.

h. To promote privacy of health information a login will be required for access to app (created upon e-consent) and the iPhone will be set to password protected mode / touch ID activated

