- v. After study completion, participants will participate in a phone interview, if they agree, to gather more information about their experience, using a standardized set of questions (see Supplemental Study Documents).
- w. Participants may be given the option to participate in future research studies.

Data collection for the Corrie Digital Health group and the historical standard of care comparison group to assess the primary outcome:

- a. Following study completion, we will submit requests to Johns Hopkins Hospital and Johns Hopkins Bayview Medical Center, Massachusetts General Hospital Partners group, and Reading Hospital administrative data managers to obtain the following data on both groups: age, sex, race, language, body mass index, marital status, smoking status, diagnosis of STEMI versus NSTEMI, insurance status (payor index), admission date, discharge date, type of intervention received in hospital (PCI or CABG), a discrete count of AHRQ identified Elixhauser comorbidities based on ICD-9-CM and ICD-10 diagnosis codes, discharge disposition, readmission, days to readmission, reason for readmission, ED visits, observation visits, and mortality.
- b. These variables will be obtained for both groups via the administrative databases to ensure standardization of variables and collection.
- c. For the historical control group we will query data for patients admitted to each hospital from October 1, 2015 to October 1, 2016 for a STEMI or NSTEMI. To obtain data for the Corrie Digital Health group, 30 days after the last enrolled participant is discharged from the hospital, we will send a list of

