Study duration	Each participant will join the study for the entirety of their hospitalization following enrollment. This inpatient phase will last approximately 1 to 5 days, depending on the length of stay and the enrollment date, with the goal being to enroll the patient participant as early as possible in his/her hospitalization. Then enrollment will continue for 30 days following discharge for an approximate study duration of 30 to 40 days.
Routine care	Same as for primary cohort
Treatment failure or participant removal criteria	None (same as for primary cohort)
Participants receiving therapy when study ends or if a participant’s participation in the study ends prematurely	Same as for primary cohort
Procedural steps	Same as for the Corrie Digital Health group in the primary cohort, paragraphs a through n, and r through w. The Reading cohort will not participate in the procedural steps for the 6 and 12-month follow-ups, as described in paragraphs p and q.

	Data collection for the Corrie Digital Health group and the historical standard of care comparison group to assess the primary outcome will be the same.
--	--

5. Inclusion/Exclusion Criteria

a) The Corrie Digital Health group

Inclusion Criteria	Exclusion Criteria
-Patient admitted for acute myocardial infarction; MI present at the time of admission and Type I NSTEMI or STEMI -18 years or older - smartphone ownership	-Non-English speaking -Visual, hearing, or motor impairment which precludes use of the intervention -Persons not able to participate on due to severity of illness (e.g., intubated and on sedation in the setting of cardiogenic shock)

b) The Historical Comparison group

Inclusion Criteria	Exclusion Criteria
-Patient admitted for acute myocardial infarction; MI present at the time of admission and NSTEMI or STEMI -18 years or older	-Non-English speaking

6. Drugs/ Substances/ Devices

- a. The rationale for choosing the drug and dose or for choosing the device to be used.
- b. Justification and safety information if FDA approved drugs will be administered for non-FDA approved indications or if doses or routes of administration or participant populations are changed.
- c. Justification and safety information if non-FDA approved drugs without an IND will be administered.

Devices: Smartphone + Apple Watch + Silicone HealthBand + iHealth BP monitor +/- Apple TV

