Statistical plan including sample size justification and interim data analysis.	
Allowing for 10% of drop-outs during 30-day follow-up, the aim was to recruit N=200 in the intervention group and N=1,000 patients in the comparison group to provide around 90% power at the 2-sided 5% level of significance to detect a hazard ratio of 0.5 (ie, 50% reduction in a hazard of the intervention group), assuming 85% of patients in the comparison group survive or are not readmitted by the end of study (Stata stpower). The incident readmission rate of patients in our historical comparison group admitted to JHH and JHBMC was 16 cases per 100 person-months. We aim to detect a 50% risk reduction in readmission rates because our solution is comprehensive in nature and it is estimated that 76% of 30-day readmissions are potentially preventable using proven standards of care.
 
Our statistics will be primarily descriptive. We will examine characteristics of participants who join the study including demographics (e.g., age, sex, race/ethnicity, level of education, mHealth literacy, body mass index, marital status, occupation, annual income, insurance coverage) and clinical characteristics (e.g., severity of MI by TIMI/GRACE score, Killip Class, severity of cardiovascular disease by ejection fraction, medications, cardiac risk factor profile including dyslipidemia and lipid management characteristics as above), hypertension, diabetes, smoking, prior history of MI, and other comorbidities such as COPD, anxiety, and depression. We will examine primary and secondary outcomes as frequencies (percentage) for categorical variables and mean (SD) for continuous variables according to site of enrollment (JHH or JHBV) and type of mobile device (iPhone or Android). We will compare baseline characteristics of study participants using χ^2 and t-tests for categorical and continuous variables, as appropriate.
 
In assessing readmissions and cost-effectiveness, concurrent and historical controls will be matched to enrolled patients based on sociodemographic/clinical variables, and risk stratification using APR DRG / severity of illness scores (which are shown in the literature to be predictive for readmissions). We will conduct a Cox survival analysis to compare time to first readmission between the Corrie digital health group and the historical comparison group. We will build a Markov model of cost-effectiveness with the perspective of a hospital adopting Corrie technology, taking into account the lifelong outcome and cost of the Corrie discharge process versus the standard

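### The data request behind the primary comparison carries payor as its only direct socioeconomic field, so the promised sociodemographic matching can balance socioeconomic status only through payor and indirect proxies

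*Combined protocol and SAP*

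**What the plan says.** - **Fields for both groups.** Section 4, data collection for the primary outcome, item a, lists "age, sex, race, language, body mass index, marital status, smoking status, diagnosis of STEMI versus NSTEMI, insurance status (payor index"). It continues with "admission date, discharge date, type of intervention received in hospital (PCI or CABG), a discrete count of AHRQ identified Elixhauser comorbidities", then disposition and outcomes. No income, education, occupation, address, ZIP code or area index appears.
- **Source.** Item b of the same list states: "These variables will be obtained for both groups via the administrative databases to ensure standardization of variables and collection".
- **Matching.** Section 7 says that "concurrent and historical controls will be matched to enrolled patients based on sociodemographic/clinical variables", together with APR DRG or severity scores. It does not say which sociodemographic variables are meant, and the Cox model that follows names no covariates.
- **Socioeconomic detail.** Section 7 also names "level of education, mHealth literacy, body mass index, marital status, occupation, annual income, insurance coverage", but as characteristics of the patients who join the study.
- **Eligibility.** Section 5a requires "smartphone ownership" for the Corrie group. Section 5b, for the historical group, asks only for "MI present at the time of admission and NSTEMI or STEMI -18 years or older" and excludes non-English speakers.
- **Device loan.** For patients who do not own an iPhone, Section 4 step b says that "we loan an iPhone along with the Apple Watch during the study period". This is conditional on resources.
- **Selection-bias data.** The list for the 541 ineligible or declined patients (Section 4, Hopkins sites only) again has payor as its only direct socioeconomic field.

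**The concern.** There is no randomisation, so the primary hazard ratio is protected only by how well matching and modelling make the two groups alike. One group is screened on owning a smartphone and agreeing to use an app. The other is taken from records with no such screen. It is reasonable to expect that the screen selects partly on socioeconomic status, although the documents do not say so. The plan's most direct measures of that status (education, occupation, income) exist in one group only, and a variable without a counterpart in the controls can serve neither for matching nor for adjustment. If Corrie patients are better off in ways that payor, race, marital status and age do not capture, and if better-off patients are readmitted less, the difference is credited to the app. A larger sample would not remove it.

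**Working it through.** **1. The plan's own figure.** Inputs from Section 7: 200 v 1,000 patients, hazard ratio 0.5, two-sided 5%, 85% of the comparison group event-free, 10% drop-out, power around 90%.
- Corrie event-free proportion: 0.85^0.5 = 0.922.
- After 10% loss (180 v 900): events = 180 × 0.078 + 900 × 0.15 = about 149.
- Schoenfeld power = Φ(√(149 × 1/6 × 5/6) × ln 2 − 1.96) = 88.4%. Without loss there are 165.6 events and power is 91.4%.

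The stated power is reproduced. The point concerns missing covariates and disputes no design figure.

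**2. What is held in each group.**

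| Item | Corrie | Historical controls |
|---|---|---|
| Payor | yes | yes |
| Age, race, marital status | yes | yes |
| Education, occupation, income | planned (Section 7) | not requested |
| Area-level measure or ZIP code | not requested | not requested |
| Smartphone | entry criterion | not a criterion, not requested |

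**3. Size of an uncorrected imbalance.** The documents give no figure for this, so the inputs are assumptions shown as a range. Let pH and pC be the proportions of disadvantaged patients among controls and Corrie patients, and RR their relative readmission hazard. With no app effect and no adjustment,

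spurious HR = (1 − pC + pC × RR) / (1 − pH + pH × RR).

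| pH v pC | RR 1.3 | RR 1.6 |
|---|---|---|
| 40% v 20% | 1.06/1.12 = 0.946 | 1.12/1.24 = 0.903 |
| 50% v 15% | 1.045/1.15 = 0.909 | 1.09/1.30 = 0.838 |

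**4. If the requested fields remove half the gap** (a further assumption):

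| pH v residual pC | RR 1.3 | RR 1.6 |
|---|---|---|
| 40% v 30% | 1.09/1.12 = 0.973 | 1.18/1.24 = 0.952 |
| 50% v 32.5% | 1.0975/1.15 = 0.954 | 1.195/1.30 = 0.919 |

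**5. Effect on the test.** With no app effect and 15% failing in all 1,080 patients there are 162 events. The standard error of the log hazard ratio is 1/√(162 × 1/6 × 5/6) = 1/√22.5 = 0.211. The unadjusted values in step 3 then lead to rejection about 6% (HR 0.946) to 13% (HR 0.838) of the time, instead of 5%.

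**6. Effect on a result at the design value.** An observed 0.5 would correspond to 0.5/0.946 = 0.53 at the mild end and 0.5/0.838 = 0.60 at the severe end.

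**The case against.** The strongest reply has five parts.

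- **Balance is not absent.** A reader might infer that the comparison cannot balance socioeconomic status at all. The documents do not support that. Payor, race, marital status and age are requested for both groups and allow partial, indirect balance. This stands.
- **The list may be incomplete.** Section 7 relies on APR DRG, which item a does not list, and item d is a second extraction covering both groups. Neither closes the gap: APR DRG measures severity, and item d is lipid-focused and limited to Hopkins. Section 7 also mentions concurrent controls, but Section 4 describes no separate data request for them.
- **The iPhone loan eases the selection.** It may, but it is offered only as resources allow, and Section 5a still lists smartphone ownership.
- **The link from smartphone to wealth is inferred.** True. Ownership may also follow age, which is collected. A reader might add that payor discriminates poorly among older patients, or that the groups differ in how far they live from the hospital. The documents give no age, payor or distance distribution, so neither argument is used here.
- **The remedy is a proxy, and some data are already held.** Both are right. An area measure does not reveal who owned a smartphone in 2015-16. Section 7 already quotes a readmission rate for the Hopkins historical group, so at least part of the control data seems to have been drawn.

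These points limit the size and wording of the concern. They do not supply a direct socioeconomic measure other than payor for the controls.

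**Conclusion.** The point holds in a limited form. In the request that feeds the primary comparison, payor is the only direct socioeconomic field, so the matching promised in Section 7 can reach socioeconomic status only through payor and indirect proxies. Any remaining imbalance would plausibly favour the app. This direction rests on two inferences that the documents do not state: that owning a smartphone goes with being better off, and that being better off goes with fewer readmissions.

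The unadjusted illustration gives a spurious hazard ratio of 0.95 to 0.84 across the assumed inputs. Bias left after matching should be smaller, to the extent that the requested fields track disadvantage. A reader might infer that such bias could produce the hazard ratio of 0.5 that the study is designed to detect. It could not do so alone within these ranges: even the most severe unadjusted case would turn an observed 0.5 into about 0.60. The change is worth making because it is cheap and the comparison has no randomisation to fall back on.

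**What to change.** - Add to item a, for the Corrie and historical groups, an area-deprivation or median-income quintile that the hospital data managers derive from home ZIP code at the index admission. Requesting the ZIP code itself is the alternative.
- Add the same field to the list for the 541 ineligible or declined patients, so that the selection-bias comparison can use it.
- Name the quintile in Section 7 as a matching variable and as a covariate in the Cox model.

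**Cost.** The data managers take on a small extra step. A supplementary pull is needed wherever control data are already held. If the ZIP code itself is released, it must be handled as an identifier; returning only the quintile avoids this. The quintile is an imperfect proxy for individual circumstances and leaves smartphone ownership unmeasured in the controls, so the report should still state that limitation.

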	
participant identifiers to the hospital data managers.
 
d. In an ancillary study restricted to both groups of Hopkins participants, we will perform an Epic data extraction focused on measures of 2018 AHA/ACC guideline-directed cholesterol management such as serum lipid values upon admission through 12 months of hospital discharge, whether patients were on lipid lowering therapy at the time of admission, prescription of lipid lowering therapies at the time of discharge including statins and non-statins, whether the statin was a high intensity statin regimen at the time of hospital discharge, if patients were not on statin therapy due to a history of side effects, very high risk vs not very high risk status, and whether additional lipid lowering therapies were prescribed within 12 months of hospital discharge.
 
Data collection for patients who were deemed ineligible/declined to participate in the Corrie Digital Health group to assess selection bias:
 
a. Following study completion, we will submit requests to Johns Hopkins Hospital and Johns Hopkins Bayview Medical Center administrative data managers to obtain the following data on the 541 patient who were deemed ineligible/declined to participate in the Corrie intervention group: age, sex, race, marital status, smoking status, diagnosis of STEMI versus NSTEMI, insurance status (payor index), readmission, days to readmission, and reason for readmission.
 
b. These variables will be obtained via the administrative databases to ensure standardization of variables and collection to those who were enrolled in the Corrie intervention group.

--	--

MiCORE Reading Hospital cohort:

Reading Hospital is participating in this study through a grant from the Reading Hospital Foundation. The participation of patients recruited from Reading will be limited to the 30-day (approximate) initial enrollment period. The data collected from this cohort will be used to support the study’s primary outcome: 30-day readmission rate.

Study procedures for Reading Hospital	
Study design	Same as for primary cohort

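### Comorbidity is requested for both groups only as an Elixhauser count, so the mix of conditions in the historical group cannot be checked or adjusted for from the data as requested

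*Combined protocol and SAP*

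**What the plan says.** Section 4 (Study Procedures), data collection for the primary outcome, item a, lists the variables to be requested on the Corrie and historical groups. The only general comorbidity item is "a discrete count of AHRQ identified Elixhauser comorbidities based on ICD-9-CM and ICD-10 diagnosis codes". Smoking status, body mass index, STEMI versus NSTEMI and PCI or CABG are listed as separate variables. Item b gives the reason for a common source: "These variables will be obtained for both groups via the administrative databases to ensure standardization of variables and collection". Item d adds a second two-group source at some sites: "In an ancillary study restricted to both groups of Hopkins participants, we will perform an Epic data extraction". It covers lipid values, lipid-lowering therapy and a very-high-risk classification.

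Section 7 (Study Statistics), statistical plan, opens its list of baseline variables with "We will examine characteristics of participants who join the study". Among the clinical characteristics it names "hypertension, diabetes, smoking, prior history of MI, and other comorbidities such as COPD, anxiety, and depression". It goes on: "We will compare baseline characteristics of study participants using" chi-square and t-tests, without saying which groups are compared. For readmissions and cost-effectiveness, "concurrent and historical controls will be matched to enrolled patients based on sociodemographic/clinical variables" and on APR DRG / severity of illness scores. The Cox comparison of Corrie with historical patients names no covariates.

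**The concern.** The primary comparison sets app users against patients admitted in 2015–2016, so its credibility rests on measured baseline data. Section 5 selects the two groups differently. Corrie patients need a smartphone, a Type I NSTEMI or a STEMI, no impairment that precludes use of the intervention, and an illness not too severe to take part. Historical patients need only be English-speaking adults with NSTEMI or STEMI.

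A count gives every condition equal weight. Two groups with the same average count may carry different conditions, and those conditions may differ in how strongly they predict early readmission. If only the count is held for historical patients, such a difference cannot be tabulated or adjusted for, and nobody can show that it is absent. The conditions that the plan itself regards as worth describing would be known in one group and unknown in the other.

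**Working it through.** **Step 1. Section 7 set against the data sources for historical patients.**

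| Characteristic in section 7 | Individual source for historical patients |
|---|---|
| Smoking | Item a, all sites in the request |
| Dyslipidemia and lipid management | Item d, Hopkins only |
| Hypertension, diabetes, prior MI, COPD, anxiety, depression | None listed; at most, inside the item a count |
| APR DRG / severity of illness (for matching) | None listed |

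The documents do not say which conditions enter the count. It therefore cannot be confirmed that all six named conditions contribute to it.

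**Step 2. The plan's power figure, to see whether it is affected.** Inputs from section 7: 200 and 1,000 patients, 10% drop-out, 85% event-free in the comparison group, hazard ratio 0.5, two-sided 5%.

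- After drop-out: 180 and 900 patients, with 1/6 of them in the Corrie group.
- Expected events: 900 × 0.15 + 180 × (1 − √0.85) = 135 + 14.0 = 149.
- Schoenfeld power: Φ(√(149 × 1/6 × 5/6) × ln 2 − 1.96) = Φ(1.19) = 0.88. Without drop-out it is 0.91.

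This agrees with the stated figure of around 90%. Nothing in it depends on which comorbidity variables are collected.

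**Step 3. How large could hidden confounding be?** The documents give no prevalences or risk ratios by condition, so every input here is an assumption. For one condition with risk ratio RR and prevalence p1 (Corrie) and p0 (historical), the spurious risk ratio with no app effect is (1 + p1(RR − 1)) / (1 + p0(RR − 1)).

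- Condition A, RR 2, 20% versus 30%: 1.20/1.30 = 0.92.
- Condition A, RR 2, 20% versus 40%: 1.20/1.40 = 0.86.

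These two figures are incomplete. If the average counts are equal, a deficit in A must be matched by an excess elsewhere. Add condition B at 40% versus 30%, taken as independent of A. The two conditions then contribute 0.20 + 0.40 = 0.60 per Corrie patient and 0.30 + 0.30 = 0.60 per historical patient, so the counts agree.

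- A with RR 2, B with RR 1.5: (1.20/1.30) × (1.20/1.15) = 0.923 × 1.043 = 0.96.
- Risk ratios exchanged, A with RR 1.5 and B with RR 2: (1.10/1.15) × (1.40/1.30) = 0.957 × 1.077 = 1.03.

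With counts balanced exactly, the spurious ratio falls on either side of 1, depending on which condition is the stronger predictor.

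**Step 4. How many covariates could be used?** After drop-out the Corrie group yields about 14 events under the target effect, or 180 × 0.15 = 27 under no effect. That is too few to support a long list of separate matching variables.

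**The case against.** The strongest reply is that section 7 promises no between-group use of these conditions. The list is introduced as a description of patients who join the study. It also holds education, mHealth literacy, occupation and income, none of which is in item a, and the next sentence splits outcomes by enrolment site and device type. That is a fair reading. The plan uses the word participants for historical patients elsewhere (the routine care row of section 4, and data-collection item d), so the chi-square and t-test sentence is ambiguous. A reader might infer that the plan breaks a commitment to compare or match on the individual conditions. The text does not go that far.

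Three further objections stand:

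- Matching is not on the count. It is on unspecified clinical variables plus APR DRG / severity of illness, so the plan does not treat patients with equal counts as interchangeable. That protection is weaker than it looks, because the score is not in the item a list.
- Item a is not the only source for historical patients. Item d adds lipid data and a risk classification, though at Hopkins only, and these do not supply the six conditions.
- The conditions are not shown to be lost. The count is built from diagnosis codes in the hospital databases, so they can be asked for. The limitation lies in the request as worded.

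It can also be said that a count is a compact summary and that matching on every flag would be worse. Given the number of events, that is a reasonable view, and it argues against replacing the count in the matching.

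**Conclusion.** The point holds as a gap in the data request. From the data as requested, six conditions that section 7 names cannot be tabulated or adjusted for in the historical group. The severity score named for matching has no listed source either. In a non-randomised comparison with unequal eligibility, this leaves room for residual confounding that could not be seen.

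Its direction and size are unknown. A reader might infer that the gap favours the app because Corrie patients had to be well enough to use it, and that several such conditions would compound. The documents do not show this. At equal counts, deficits in some conditions force excesses in others, and the illustrations run from 0.92 (offset ignored) through 0.96 to 1.03 on assumed inputs. Even 0.86, the largest departure shown, would not by itself produce the targeted hazard ratio of 0.5, though it would distort the estimate. This is a correctable weakness in confounding control. It does not invalidate the design.

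**What to change.** Reword data-collection item a in section 4 to request, for both groups:

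- a yes/no flag for each Elixhauser comorbidity;
- the index-admission diagnosis codes, to cover any named condition that has no flag of its own, as far as it was coded;
- the APR DRG / severity of illness score on which section 7 already relies.

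Derive the count from the flags. In section 7, state that the individual conditions will be tabulated by group, and name the matching variables, keeping the count and the severity score among them. Prespecify a short set of the named conditions for balance checks and for one sensitivity adjustment of the Cox model. Do not match on every flag.

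The cost is the wording of a request that the plan places after study completion, a somewhat larger extract and a little more analysis. There is no added patient contact and no change to sample size or power. Section 7 already quotes a historical readmission rate for the two Hopkins hospitals. If part of the historical extract has been drawn, those sites would need a supplementary request.
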